8. STUDY ASSESSMENTS AND PROCEDURES

Overview

All participants enrolled in the study will undergo the same study evaluations throughout the study. The Schedule of Activities (Section 1.3) summarizes the frequency and timing of efficacy, PK, biomarker, and safety measurements applicable to this study.

If multiple assessments are scheduled for the same timepoint, it is recommended that procedures be performed in the following sequence: ECGs, vital signs, blood draw. Blood collections for PK assessments should be kept as close to the specified time as possible. Other measurements may be done earlier than specified timepoints if needed. Actual dates and times of assessments will be recorded in the source documentation and eCRF.

Additional serum or urine pregnancy tests may be performed, as determined necessary by the investigator or required by local regulation, to establish the absence of pregnancy at any time during the participation in the study.

The total blood volume for first year of the study is approximately 300 mL (186 mL for safety, 84 mL for efficacy, 10 mL for PK, 16 mL for biomarkers, and 4 mL for pregnancy testing [women only]) and for second year or after is approximately 153 mL (98 mL for safety and 55 mL for efficacy).

Repeat or unscheduled samples may be taken for safety reasons or for technical issues with the samples.

Sample Collection and Handling

The actual dates and times of sample collection must be recorded in the eCRF or laboratory requisition form. Refer to the [Schedule of Activities \(SoA\)](#) for the timing and frequency of all sample collections.

Instructions for the collection, handling, storage, and shipment of samples are found in the laboratory manual. Collection, handling, storage, and shipment of samples must be under the specified, and where applicable, controlled temperature conditions as indicated in the laboratory manual.

Study-Specific Materials

The investigator will be provided with the following supplies:

- Investigator's brochure for ibrutinib
- Pharmacy manual/study site investigational product and procedures manual
- Laboratory manual
- National Cancer Institute Common Terminology Criteria for AEs (NCI-CTCAE) version 4.03
- Electronic data capture (eDC) Manual

- Imaging acquisition guideline
- Sample ICF
- Provisioned smartphone/tablet for eDiary of ibrutinib
- Barcode scanner for study drug tracking

The participation period will consist of a screening phase, a treatment phase, and a follow-up phase.

8.1. Screening Phase

The screening phase assessments will be performed ≤ 30 days prior to start of study intervention. All participants must first read, understand, and sign the Independent Ethics Committee/Institutional Review Board (IEC/IRB) approved ICF before any study-specific screening procedures are performed. In this study, eligible participants will have clinicopathological diagnoses of WM in accordance with the consensus panel of the second IWWM. Pathologic diagnosis will also be reviewed by a central pathologist (see Section 8.4.7).²⁸

8.1.1. Screening Visit

The following procedures will be performed at the screening visit within 30 days prior to first dose of ibrutinib unless otherwise noted:

- Confirm eligibility (per Inclusion/Exclusion Criteria) and enroll. Dosing should occur within 3 days of enrollment
- Medical history including demographic information
- A complete physical examination including general appearance of the participant, height, weight, and examination per clinical practice
- Evaluation of ECOG performance status
- Obtain vital signs (including blood pressure, pulse rate, respiratory rate, and body temperature) after the participant has rested in the sitting position for at least 5 minutes
- Obtain a single 12-lead ECG after the participant has been in a supine position and resting for at least 5 minutes
- Record AEs since signing the ICF
- Record concomitant medication history including over-the-counter drugs, vitamins, and herbs
- Imaging by CT of the neck, chest, abdomen, and pelvis should be obtained during screening (within 42 days before the first dose of ibrutinib)
- Obtain a bone marrow aspirate and biopsy (if not performed within 60 days prior to first dose of ibrutinib)
- Obtain blood specimens for the following laboratory tests:
 - Hematology
 - Serum chemistry

Coagulation studies (prothrombin time [PT], INR, and aPTT)

- Hepatitis serologies
- Serum viscosity
- Serum protein electrophoresis (SPEP)
- Quantitative serum IgS (IgA, IgG, and IgM)
- Serum free light chain assay
- Serum immunofixation
- β 2-microglobulin

- Obtain serum pregnancy test for women of childbearing potential only

8.2. Treatment Phase

The treatment phase will extend from first dose of ibrutinib until the EOT visit (which should occur after 30 days of last dose of ibrutinib or prior to the start of a new anticancer treatment). All participants will receive IV administration of rituximab weekly for 4 consecutive weeks, followed by a second course of IV rituximab administered weekly for 4 consecutive weeks after a 12-week interval. All participants will receive oral ibrutinib daily and continuously until criteria for permanent discontinuation of ibrutinib are met (see Section 7.1, Discontinuation of Study Intervention). Response assessments will be performed using the modified consensus criteria adapted from the sixth IWWM (NCCN version 2, 2019).²⁷ Participants with confirmed PD must discontinue the study intervention.

8.2.1. Week 1

Predose

- Complete physical examination including general appearance of the participant, weight, and examination per clinical practice
- ECOG performance status
- Vitals signs including blood pressure, pulse rate, respiratory rate, and body temperature
- Collect blood samples for the following laboratory tests:
 - Hematology
 - Serum chemistry
 - Serum protein electrophoresis (SPEP)
 - Quantitative serum IgS (IgA, IgG, and IgM)
 - Biomarkers
- Obtain urine pregnancy dipstick test for women of childbearing potential only prior to first dose. If the test result is positive, the investigator should discuss with Medical Monitor and/or gynecologist and the pregnancy must be ruled out by ultrasound to be eligible
- Review of AEs and concomitant medications
- Review Inclusion and Exclusion Criteria to confirm participants' eligibility prior to dosing

Dosing and Postdose

- Dispense ibrutinib
- Administration of ibrutinib
- Administration of rituximab
- Review of AEs and concomitant medications

8.2.2. Weeks 2, 3, and 4

- Collect blood sample for quantitative serum IgS (IgA, IgG, and IgM) (sampling at predose only for week 4)
- Blood sampling for PK evaluation (Week 4 only, postdose as described in [Table 6](#))
- Administration of rituximab and ibrutinib
- Review of dosing compliance (in APP)
- Review of AEs and concomitant medications

8.2.3. Weeks 5, 9 and 13

- Dispense ibrutinib
- Continuous daily dosing of ibrutinib
- Symptom-directed physical examination and review of symptoms should include inquiry of ocular symptoms
- ECOG performance status
- Vitals signs including blood pressure, pulse rate, respiratory rate, and body temperature
- Collect blood samples for the following laboratory tests:
 - Hematology
 - Serum chemistry
 - Serum protein electrophoresis (SPEP)
 - Quantitative serum IgS (IgA, IgG, and IgM)
 - Overall disease assessment
 - Review of AEs and concomitant medications

8.2.4. Week 17**Predose**

- Symptom-directed physical examination and review of symptoms should include inquiry of ocular symptoms
- ECOG performance status
- Vitals signs including blood pressure, pulse rate, respiratory rate, and body temperature

- Collect blood samples for the following laboratory tests:
 - Hematology
 - Serum chemistry
 - Coagulation studies (PT, INR, and aPTT)
 - Serum protein electrophoresis (SPEP)
 - Quantitative serum IgS (IgA, IgG, and IgM)
- Follow-up CT scan for all participants with measurable nodal/extranodal disease during screening
- Overall disease assessment
- Review of AEs and concomitant medications
- Review of dosing compliance (in APP)

Dosing and Postdose

- Dispense ibrutinib
- Administration of ibrutinib and rituximab
- Review of AEs and concomitant medications

8.2.5. Weeks 18 to 20

- Administration of ibrutinib and rituximab
- Review of dosing compliance (in APP)
- Review of AEs and concomitant medications

8.2.6. Week 21

- Dispense ibrutinib
- Continuous daily dosing of ibrutinib
- ECOG performance status
- Vitals signs including blood pressure, pulse rate, respiratory rate, and body temperature
- Symptom-directed physical examination and review of symptoms should include inquiry of ocular symptoms
- Collect blood samples for the following laboratory tests:
 - Hematology
 - Serum chemistry
 - Serum protein electrophoresis (SPEP)
 - Quantitative serum IgS (IgA, IgG, and IgM)
- Overall disease assessment

- Review of AEs and concomitant medications

8.2.7. Week 25 Onwards Until PD or Unacceptable Toxicity (Every 8 Weeks)

- Dispense ibrutinib
- Continuous daily dosing of ibrutinib
- ECOG performance status
- Vitals signs including blood pressure, pulse rate, respiratory rate, and body temperature
- Symptom-directed physical examination and review of symptoms should include inquiry of ocular symptoms
- Collect blood samples for the following laboratory tests:
 - Hematology
 - Serum chemistry
 - Serum protein electrophoresis (SPEP)
 - Quantitative serum IgS (IgA, IgG, and IgM)
 - Serum free light chain assay (Week 57 only)
- Follow-up CT scans should be performed at Week 57 for each participant. Other follow-up CT scan will be required at Weeks 33, 49, and every 24 weeks after Week 57 for all participants with measurable nodal/extranodal disease during screening
- Bone marrow aspirate/biopsy will be required at any time after screening to confirm a CR
- Overall disease assessment
- Review of AEs and concomitant medications

8.2.8. Suspected PD Visit

The suspected PD visit should be performed at any time during the study, if based on clinical and/or laboratory evaluation, the investigator suspects PD, or if the participant discontinues treatment for any other reason. If possible, the visit should be performed within 24 hours after the participant's previous dose. The following procedures will be performed:

- Complete physical examination including general appearance of the participant, weight, and examination per clinical practice
- ECOG performance status
- Vitals signs (including blood pressure, pulse rate, respiratory rate, and body temperature)
- Collect blood samples for the following laboratory tests:
 - Hematology
 - Serum chemistry
 - Serum protein electrophoresis (SPEP)
 - Quantitative serum IgS (IgA, IgG, and IgM)

- Imaging by CT scan may be performed if clinically indicated as reason for progression
- Overall disease assessment
- Review of AEs and concomitant medications

8.2.9. End-of-Treatment Visit

An EOT visit should occur 30 days (+7 days) from the last dose of ibrutinib or prior to the start of a new anticancer treatment. If the participant starts a new anticancer treatment <7 days after the suspected PD visit, only those procedures not conducted at the suspected PD visit should be performed at the EOT visit.

The following procedures will be performed at the EOT visit:

- Complete physical examination including general appearance of the participant, weight, and examination per clinical practice
- ECOG performance status
- Vitals signs (including blood pressure, pulse rate, respiratory rate, and body temperature)
- Collect blood samples for the following laboratory tests:
 - Hematology
 - Coagulation studies (PT, INR, and aPTT)
 - Serum protein electrophoresis (SPEP)
 - Quantitative serum IgS (IgA, IgG, and IgM)
- Review of AEs and concomitant medications
- Overall disease assessment

8.3. Follow-up Phase

Once a participant has completed the EOT visit, they will enter the follow-up phase. Participants who withdraw from treatment for reasons other than PD and withdraw of consent will participate in ongoing follow-up visits.

8.3.1. Response Follow-up Visits (Until PD)

Participants who discontinue the study for reasons other than PD will be followed every 12 weeks (± 7 days) by clinic visit until PD or use of alternative anticancer therapy. During this period, the following procedures will be performed:

- Collect blood samples for the following laboratory tests:
 - Hematology
 - Serum protein electrophoresis (SPEP)
 - Quantitative serum IgS (IgA, IgG, and IgM)
- Overall disease assessment

- Survival status and new anticancer therapy use

8.3.2. Survival Follow-up Visits

After confirmed disease progression, participants will be contacted to assess survival status approximately every 12 weeks (± 7 days) by clinic visit or telephone to assess survival, the use of alternative antineoplastic therapy, and occurrence of any other malignancy until death, withdrawal of consent by participant, lost to follow-up, or study terminated by sponsor, whichever comes first.

8.4. Efficacy Assessments

Response assessments will be performed using the modified consensus criteria adapted from the sixth IWWM (NCCN version 2, 2019).²⁷

Progression of nodal and extranodal disease should be evaluated based on the revised criteria for malignant lymphoma described in the revised International Working Group for NHL.³ The spleen is considered nodal disease.

Efficacy evaluation will include the following components:

- Hematologic parameters by complete blood count (CBC)
- Quantitative serum IgS (IgA, IgG, and IgM)
- Quantitative serum-M protein (SPEP)
- Qualitative serum immunofixation, if applicable
- Radiographic evaluation, if applicable
- Bone marrow aspirate and biopsy, if applicable

If disease progression is suspected solely based on the results of a single examination or a single laboratory parameter (eg, IgM), this finding should be confirmed by a subsequent evaluation at least within 4 weeks from the first finding. Additional hematologic parameters, radiographic evaluation and bone marrow biopsy should be performed at the discretion of the treating physician to confirm PD if indicated. PD is defined as one of the following:

- A $\geq 25\%$ increase in serum IgM with a total increase of at least 500 mg/dL from nadir (Confirmation of the initial IgM increase is required when IgM is sole criterion for progressive disease.)

Note: Nadir for serum IgM is defined as the lowest serum IgM value obtained at any time from baseline onwards with the exception that serum IgM levels post-plasmapheresis will not be considered for up to 35 days.

- New symptomatic disease on the basis of malignant pleural effusion, Bing Neel (WM CNS disease) syndrome, amyloidosis or light chain deposition disease, or other paraprotein mediated disorder.
- New or recurrent involvement in the bone marrow

- Measurable nodal and extranodal disease will follow the definition of nodal progression by imaging in Section 8.4.6.1
- Appearance of new splenomegaly or $\geq 50\%$ increase from nadir in enlargement of the spleen
- Appearance of new extranodal disease

In general, participants should continue study intervention until progression is confirmed by a serial examination within 4 weeks from the first finding and confirmation by the investigator. When disease progression has been confirmed by the investigator, study intervention should be discontinued. Once the investigator has confirmed disease progression, participants should continue to adhere to all other study-related procedures. Whenever possible, subsequent anticancer therapy should not be initiated until disease progression is confirmed by the investigator.

If at any time CR is suspected (serum IgM values in normal range and disappearance of the SPEP), all assessments including serum immunofixation, bone marrow assessment and radiographic evaluation (if nodal/extranodal disease is present at baseline) must be performed according to the IWWM response assessment guidelines.

The determination of disease status for continuation of treatment will be assessed by the investigator at the site based on the results of the efficacy assessments. For the primary endpoint, response to treatment or progression will be determined based on radiographic evaluations as assessed by independent radiologist and the overall response assessment will be performed by an independent oncologist (ie, IRC). The process and convention of the IRC will be detailed in a separate charter.

8.4.1. Quantitative Serum Immunoglobulins

Testing for IgA, IgG and IgM levels will be performed by central laboratory.

8.4.2. Serum Immunofixation

Samples will be collected and sent to a central laboratory. Repetitive immunofixation on study is only required to confirm a CR (conducted on the first observation that the participant has no detectable monoclonal protein) and then repeated at every study visit until disease progression.

8.4.3. Serum Protein Electrophoresis (SPEP)

Sample(s) will be sent to a central laboratory to quantify the serum-M protein.

8.4.4. Serum Free Light Chain Assay

Sample(s) will be sent to a central laboratory for measurement of Ig-free light chains in serum.

8.4.5. Serum Viscosity

Additional assessments may be performed if clinically indicated during the course of the study. Sample(s) will be sent to a central laboratory for measurement of serum viscosity in serum.

8.4.6. Radiographic Imaging

Pretreatment tumor assessment will be performed up to 42 days before the first dose of ibrutinib. Lesions that have been irradiated cannot be included in the tumor assessment unless unequivocal tumor progression has been documented in these lesions after radiation therapy.

A CT scan (with contrast unless contraindicated) of the neck, chest, abdomen, and pelvis must be performed. Information on extranodal involvement will also be recorded.

In the case where CT with contrast is not applicable, an alternative would be a CT without contrast, or an MRI of the abdomen and pelvis and a CT of the chest without contrast.

NOTE: Positron emission tomography (PET)/CT hybrid scanners may be used to acquire the required CT images only if the CT produced by the scanner is of diagnostic quality, adheres to the specified slice thickness/scan parameters, and includes the use of IV contrast. Imaging data will be sent to IRC and reviewed centrally.

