- g. Women of childbearing potential only. Highly sensitive serum (β human chorionic gonadotropin [β hCG]) pregnancy test required at screening and urine pregnancy test required at Day 1 prior to first dose. If the test result is positive, the investigator should discuss with Medical Monitor and/or gynecologist and the pregnancy must be ruled out to be eligible.
- h. Participants who are positive for Hepatitis C antibody should have documented 24 weeks of sustained virologic response in order to be eligible for the study.
- i. Subsequent Serum viscosity (after screening) should be performed at the discretion of the treating physician in any participant with signs and symptoms suggesting a hyperviscosity syndrome.
- j. Repetitive serum immunofixation on study is only required to confirm a complete response (conducted on the first observation that the participant has no detectable monoclonal protein) and then repeated at every study visit until disease progression.
- k. Pharmacokinetic samples will be drawn for all participants according to the schedule in Section 8.8.2.
- l. These parameters will be used to assess possible tumor flare (IgM flare) after initiating treatment for safety observations.
- m. CT scans of the neck, chest, abdomen, and pelvis should be obtained during screening (up to 42 days before first dose) for each participant.
- n. Follow up CT scans should be performed at Week 57 for each participant. Other follow up CT scans will be required at Weeks 17, 33, 49, and every 24 weeks after Week 57 for all participants with measurable nodal/extranodal disease during screening. Additional assessments may be performed if clinically indicated during the course of the study at any time.
- o. CT scan at suspected PD visit may be performed if clinically indicated as reason for progression.
- p. Bone marrow aspirate and biopsy will be required at any time after screening to confirm a complete response. A clinical sample up to 60 days before first dose of ibrutinib can be used. A portion of these samples may be used for biomarker assessments.

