8.4.6.1. Radiographic Assessment

Progression of nodal and extranodal disease should be evaluated based on the revised criteria for malignant lymphoma described in the revised International Working Group for NHL.³ The spleen is considered nodal disease.

Up to 6 measurable lymph nodes (target lesions) should be considered if the long axis is more than 1.5 cm regardless of the short axis. If a lymph node has a long axis of 1.1 to 1.5 cm, it should only be considered abnormal if its short axis is more than 1.0 cm. Lymph nodes $\leq 1.0\text{ cm} \times \leq 1.0\text{ cm}$ will not be considered as abnormal for relapse or PD. In addition, target lesions should be clearly measurable in at least 2 perpendicular dimensions and, if possible, they should be from disparate regions of the body when these areas are significantly involved. If additional lesions are present but are not included in the target lesion assessment, they can be added as nontarget lesions followed throughout the study.

Nodal progression by imaging is defined as one of the following:

- Appearance of any new lesion more than 1.5 cm in any axis or more than 1.0 cm in short axis during or at the end of therapy, even if other lesions are decreasing in size.
- At least a 50% increase from nadir in the sum of product (SPD) of any previously involved nodes.
- At least a 50% increase from nadir in the product of a single previously involved node.

Of those, regarding a lymph node with a diameter of the short axis of less than 1.0 cm at nadir, in the product of the node must increase by $\geq 50\%$ from nadir and to a size of $1.5 \times 1.5\text{ cm}$ or more than 1.5 cm in the long axis.

At least a 50% increase in the longest diameter of any single previously identified node more than 1 cm in its short axis.

Measurable extranodal disease should be assessed in a manner similar to that for nodal disease.

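### The MRI-based alternative to contrast CT leaves out the neck, which the protocol otherwise requires to be imaged; the other alternative, CT without contrast, does not.

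*Protocol*

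**What the plan says.** Protocol Section 8.4.6 sets the rule: "A CT scan (with contrast unless contraindicated) of the neck, chest, abdomen, and pelvis must be performed". The same four regions appear for screening in Section 1.3 (footnote m: "CT scans of the neck, chest, abdomen, and pelvis should be obtained during screening") and in Section 8.1.1 ("Imaging by CT of the neck, chest, abdomen, and pelvis should be obtained during screening").

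Where contrast CT is not applicable, Section 8.4.6 gives two options joined by 'or'. The first is worded "an alternative would be a CT without contrast" and takes no region away. The second is "an MRI of the abdomen and pelvis and a CT of the chest without contrast".

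For follow-up, Section 1.3 (footnote n) states: "Follow up CT scans should be performed at Week 57 for each participant". The scans at Weeks 17, 33 and 49, and every 24 weeks after Week 57, are required only for participants whose nodal or extranodal disease was measurable at screening. Neither that footnote nor Section 8.2.7 restates the body regions.

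Under Section 8.4.6.1, nodal progression includes this criterion: "Appearance of any new lesion more than 1.5 cm in any axis or more than 1.0 cm in short axis".

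**The concern.** The MRI option conflicts with the requirement stated just before it. A site can satisfy the option as written and still leave the neck without imaging of any kind.

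The neck is a nodal region, and three of the protocol's rules depend on knowing at baseline which nodes are present: who gets the intermediate scans, who needs radiology to confirm a CR, and what counts as a new lesion. A gap at screening can therefore cause missed disease, or a node that was there all along can be read as progression. At stake are IRC-assessed PFS, the completeness of CR confirmation, and the discontinuation of study intervention for confirmed progression.

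Use of the alternatives is foreseeable. Section 5.1 admits participants with creatinine clearance down to 30 mL/min, and its qualifying criteria for symptomatic disease include WM-related nephropathy and symptomatic or bulky lymphadenopathy.

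**Working it through.** The point rests on no figure in the plan, so the check compares the texts.

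**Step 1: regions covered.**
- Required (Sections 8.4.6, 1.3 and 8.1.1): neck, chest, abdomen, pelvis = 4.
- First alternative, CT without contrast: no region removed, so 4 on the natural reading.
- Second alternative, MRI plus chest CT: abdomen, pelvis, chest = 3. The neck is missing.
- PET/CT hybrid scanners, also in Section 8.4.6: allowed only with IV contrast, so no route for these participants.

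The gap is 4 − 3 = 1 region, and it lies in the second alternative only.

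**Step 2: the neck is not imaged at screening.**
- *Intermediate scans.* If the cervical nodes are the participant's only measurable nodal or extranodal disease, the participant is classed as having none. The scans at Weeks 17, 33 and 49 are then not required, and the first mandatory follow-up scan is at Week 57. The scans every 24 weeks after Week 57 are not required either.
- *CR check.* Section 8.4 asks for radiographic evaluation of a suspected CR only if nodal or extranodal disease was present at baseline. Cervical disease that was never imaged does not trigger it.

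**Step 3: the neck is imaged later.** Nothing in the protocol ties follow-up regions or modality to those used at screening. A participant screened by the MRI option could have a four-region CT at Week 57, or at Week 17 if other disease was measurable. A cervical node present throughout, and above 1.5 cm in any axis or 1.0 cm in short axis, would then be seen for the first time. Section 8.4.6.1 has no exception for a region not imaged at baseline, so the node meets the new-lesion criterion.

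**Step 4: what follows from that.** Progression by IRC assessment is a PFS event (Sections 3 and 9.4.3). Progression confirmed by the investigator requires study intervention to stop (Sections 7.1 and 8.4). Section 8.4 asks for a confirming evaluation when progression rests on a single examination, but a repeat scan would show the same node and would not reveal that it predated treatment.

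**Step 5: does it reach the primary endpoint?** Section 9.4.2 defines ORR by the best overall response of confirmed CR, VGPR or PR at or before subsequent antineoplastic therapy. A false new lesion at Week 57 does not remove a response already confirmed. A CR accepted without its radiographic check changes the response category, but CR, VGPR and PR all count as responses. The protocol does not reproduce the definitions of PR and VGPR, so no route to a different responder count can be shown from it.

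**The case against.** The best defence is that the neck is nowhere waived. Section 8.4.6 says imaging "of the neck, chest, abdomen, and pelvis must be performed", the sentence on alternatives concerns modality, and a careful site could add the neck unprompted. Section 8 lists an imaging acquisition guideline supplied to sites, and IRC conventions are left to a charter. Neither is shown, and either may cover the neck and consistency over time. Imaging is also reviewed centrally, and extra scans are allowed when clinically indicated.

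Much of this stands as a limit on likelihood. Consistency of acquisition is detail that such a guideline can hold. It does not remove the conflict, because the protocol itself spells out an option that names three regions after requiring four, and a supporting document should not have to correct it.

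A reader might infer more in two ways, and the documents support neither. First, that anyone unable to have contrast loses neck imaging: the first alternative keeps it. Second, that a misclassified participant could turn the trial from success to failure, since with a target of 14 one response can matter. That is true of any single misclassification and is not derived from this mechanism. A false new lesion at Week 57 leaves an earlier confirmed response intact, and PFS is summarised only descriptively.

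**Conclusion.** The point holds as an internal inconsistency confined to the second alternative in Section 8.4.6. It is minor and cheap to correct.

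Harm is conditional. The participant must be imaged by the MRI option, the site must read it as excluding the neck, and cervical disease must be present. Losing the Week 17, 33 and 49 scans also requires that no other nodal or extranodal disease is measurable. A false new lesion also requires that the neck is imaged later.

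The protocol gives no rate for any of these conditions and no contrast threshold linked to renal function, so the number affected cannot be derived. What is exposed is IRC-assessed PFS, the stop of treatment for progression, the radiographic part of the CR check and the intermediate scans. No effect on the ORR decision is shown. The conclusion assumes that the imaging guideline and IRC charter do not already resolve the gap.

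**What to change.** Reconcile Section 8.4.6 so that the MRI option also covers the neck, for example CT of the neck and chest without contrast plus MRI of the abdomen and pelvis. Add that the same body regions are imaged at screening and at every follow-up scan, with the same modality where feasible unless a contraindication arises. That qualifier is needed because a participant may develop a contraindication to contrast during the study. Align the imaging acquisition guideline with the amended text.

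A blanket rule to discount lesions in regions not imaged at baseline is not advised: it would depart from Section 8.4.6.1 and could hide real progression. Once the neck is imaged at screening, this gap no longer creates a need for such a rule.

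The cost is about two sentences in the protocol, plus adding the neck to a chest CT already planned for the few participants who take this option.
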